12.4.3 Handling of remaining intercurrent events of primary endpoint

For the primary analysis, only CR assessments after first dose of study treatment and prior start of any other anti-neoplastic therapy or HSCT are considered. An adequate response assessment is considered any disease assessment indicating response status apart from "unknown" or "not done".

12.5 Analysis of secondary endpoints

The secondary objectives are to assess the overall response rate (ORR), CR/mCR rate, duration of CR, time to response, time to CR/mCR, duration of response, duration of CR/mCR, overall survival (OS), event free survival (EFS), progression free survival (PFS), leukemia free survival (LFS), RBC/platelets transfusion independence, changes from baseline in fatigue, pharmacokinetic and safety.

12.5.1 Efficacy and/or Pharmacodynamic endpoint(s)

12.5.1.1 Safety run-in (Part 1)

CR+mCR rate

CR+mCR rate is defined as the proportion of participants with best overall response of either complete remission (CR) or marrow complete remission as per investigator assessment (Table 8-3). CR/mCR rate will be provided with exact 95% confidence interval (Clopper CJ and Pearson ES 1934).

CR/mCR will be provided by dose level of sabatolimab.

Overall Response Rate (ORR)

ORR rate is defined as the proportion of participants with best overall response of hematological improvement (HI) or better as per investigator assessment (Table 8-3). ORR rate will be provided with exact 95% confidence interval (Clopper CJ and Pearson ES 1934).

ORR will be provided by dose level of sabatolimab.

Improvement of RBC/platelets transfusion independence

Red blood cells (RBC)/Platelets transfusion independence rate is defined as the proportion of participants having received no RBC/Platelets transfusions during at least 8 consecutive weeks (see Section 8.3.1 for details).

The number and percentage of participants will be shown for the overall FAS and then also in only those with transfusion dependence at baseline (i.e ≥ 3 units of transfusion within 8 consecutive weeks prior to start of treatment).

Percentages will be provided with exact 95% confidence intervals (Clopper CJ and Pearson ES 1934). For participants with at least one period of transfusion independence, the total duration of all transfusion independence periods will be also summarized.

The duration of the transfusion independence is defined from the end date of the last transfusion received until the date transfusions are given again or last treatment in case transfusions had not (re-)started during treatment.

The data will be summarized by dose level of sabatolimab.

Immunogenicity analysis

Immunogenicity will be characterized descriptively by tabulating ADA prevalence at baseline and ADA incidence on-treatment. The data will be summarized by dose level of sabatolimab.

12.5.1.2 Cohort 2 of Safety run-in (Part 1) and Expansion (Part 2)

CR+mCR rate

CR+mCR rate is defined as the proportion of participants treated with sabatolimab at 800 mg Q4W with best overall response of either complete remission (CR) or marrow complete remission as per investigator assessment (Table 8-3). CR/mCR rate will be provided with exact 95% confidence interval (Clopper CJ and Pearson ES 1934).

Overall Response Rate (ORR)

ORR rate is defined as the proportion of participants treated with sabatolimab at 800 mg Q4W with best overall response of hematological improvement (HI) or better as per investigator assessment (Table 8-3). ORR rate will be provided with exact 95% confidence interval (Clopper CJ and Pearson ES 1934).

Duration of CR

The duration of CR will be derived for participants treated with sabatolimab at 800 mg Q4W who achieve CR per modified IWG-MDS CHeson 2006 (prior to any new antineoplastic therapy, including HSCT) as per investigator assessment and is defined from the first occurrence of CR until relapse, progression or death due to any reason. Relapse, disease progression or death occurring after HSCT will be considered as event for the duration of CR. The date of the event will be the date of relapse, progression, death whichever occurs first. If participant did not relapse nor progressed/died, the duration of response will be censored at last adequate response assessment. If the participant has started a new antineoplastic therapy without prior documented relapse or progression, the duration of CR is censored at last adequate assessment prior to start of that therapy and thus any subsequent relapse/ progression /death not considered an event for duration of CR.

Two supplementary analyses will be performed in which (a) new antineoplastic therapy and HSCT will not be censored and not counted as an event, and (b) start of new antineoplastic therapy will be considered as an event and HSCT will not be censored and not be counted as an event.

Duration of CR will be estimated using the Kaplan-Meier Method. The median duration of CR along with 95% Confidence interval will be presented.

Duration of CR/mCR

The duration of CR/mCR will be derived for participants treated with sabatolimab at 800 mg Q4W who achieve CR or mCR (prior to any new antineoplastic therapy, including HSCT) as per investigator assessment and is defined from the first occurrence of CR or mCR until relapse, progression or death due to any reason. Relapse, progression or death occurring after HSCT will be considered as event for the duration of CR/mCR. The date of the event will be the date of relapse, progression, death whichever occurs first. If participant did not relapse nor progressed/died, the duration of CR/mCR will be censored at last adequate response assessment. If the participant has started a new antineoplastic therapy without prior documented relapse or progression, the duration of CR/mCR is censored at last adequate assessment prior to start of that therapy and thus any subsequent relapse/ progression /death not considered an event for duration of CR/mCR.

Two supplementary analyses will be performed in which (a) new antineoplastic therapy and HSCT will not be censored and not counted as an event, and (b) start of new antineoplastic therapy will be considered as an event and HSCT will not be censored and not be counted as an event.

Duration of CR/mCR will be estimated using the Kaplan-Meier Method. The median duration of CR/mCR along with 95% Confidence interval will be presented.

Duration of response

The duration of response will be derived for participants treated with sabatolimab at 800 mg Q4W who achieve HI or better (prior to any new antineoplastic therapy, including HSCT) as per investigator assessment and is defined from the first occurrence of CR, mCR, PR or HI until relapse, progression or death due to any reason.

Relapse, progression or death occurring after HSCT will be considered as event for the duration of response. The date of the event will be the date of relapse, progression, death whichever occurs first. If participant did not relapse nor progressed/died, the duration of response will be censored at last adequate response assessment. If the participant has started a new antineoplastic therapy without prior documented relapse or progression, the duration of response is censored at last adequate assessment prior to start of that therapy and thus any subsequent relapse/ progression/death not considered an event for duration of response.

Two supplementary analyses will be performed in which (a) new antineoplastic therapy and HSCT will not be censored and not counted as an event, and (b) start of new antineoplastic therapy will be considered as an event and HSCT will not be censored and not be counted as an event.

Duration of response will be estimated using the Kaplan-Meier method. The median duration of response along with 95% confidence interval will be presented.

Time to CR/mCR

The time to CR/mCR will be derived for all participants treated with sabatolimab at 800 mg Q4W and is defined from start of treatment to first occurrence of CR/mCR (prior to any new antineoplastic therapy, including HSCT). For participants who reached CR /mCR after HSCT or a new antineoplastic therapy, the time to CR/mCR will be censored at time of HSCT or initiation of new antineoplastic therapy.

Participants who did not reach CR/mCR will be censored at last adequate response assessment. For participants who progressed, died or the disease progressed to acute myeloid leukemia, the time to CR/mCR will be censored at maximum follow-up (last participant last visit).

Time to CR/mCR will be estimated using the Kaplan-Meier method. The median time to CR/mCR along with 95% confidence interval will be presented.

Event-free survival (EFS)

Event-free survival (EFS) is defined from the date of start of treatment to:

- Lack of complete remission within the first 6 cycles of start of treatment
- Progression/Relapse
- Death from any cause

whichever occurs first.

Participants treated with sabatolimab at 800 mg Q4W who failed to achieve CR within 6 cycles of treatment will have their EFS event documented at start of treatment. If participant discontinued treatment due to any reason (including death) prior to 6 cycles and without CR will be considered as EFS event documented at start of treatment date.

Progression/Relapse, death events after HSCT and transfusion of blood products will be taken into account. However, Progression/Relapse, death occurring after initiation of new antineoplastic therapy will not be considered as event and EFS will be censored at last adequate response assessment.

In case of two or more missing assessments prior to documented progression, relapse or death, EFS will be censored at the last adequate response assessment prior to the documentation of relapse or death.

EFS will be estimated using the Kaplan-Meier method. The median EFS along with 95% confidence interval will be presented.

Progression free survival (PFS)

PFS is defined as the time from start date of treatment to date of relapse, progression (including transformation to acute leukemia per WHO 2016 classification) or death due to any cause. If a participant is not known to have relapsed progressed nor died, PFS will be censored at the last adequate response assessment (on or before the cut-off date). Progression/relapse or death after HSCT, interruptions, or discontinuation of study treatment due to any reason will be taken into account. However, Progression/Relapse, death occurring after initiation of new antineoplastic therapy will not be considered as event and PFS will be censored at last adequate response assessment.

In case of two or more missing assessments prior to documented progression, relapse or death, PFS will be censored at the last adequate response assessment prior to the documentation of progression, relapse or death.

PFS will be estimated using the Kaplan-Meier method. The median PFS along with 95% confidence interval will be presented.

Leukemia free survival (LFS)

LFS is defined as the time from start of treatment to transformation to acute leukemia as per investigator assessment defined as the following:

- $\geq 20\%$ blasts in bone marrow/ peripheral blood (per WHO 2016 classification)
- Diagnosis of extramedullary acute leukemia
- Death due to any cause

whichever occurs first.

If a participant is known to not have progressed to leukemia, then LFS will be censored at the last bone marrow/peripheral blood assessments (on or before the cut-off date). All of three events ($\geq 20\%$ blasts in bone marrow/peripheral blood, diagnosis of extramedullary acute leukemia or death) after HSCT, interruptions, or discontinuation of study treatment due to any reason will be taken into account. However, events occurring after initiation of new antineoplastic therapy will not be considered as event and LFS will be censored at last assessment of bone marrow/peripheral blood, diagnosis of extramedullary acute leukemia or survival follow-up prior to initiation of new antineoplastic therapy.

LFS will be estimated using the Kaplan-Meier method. The median LFS along with 95% confidence interval will be presented.

Overall Survival (OS)

OS is defined as the time from start date of treatment to date of death due to any cause. If a participant is not known to have died, then OS will be censored at the latest date the participant was known to be alive (on or before the cut-off date). All deaths will be taken into account whenever the death occurred, i.e. even after new anti-neoplastic therapy, HSCT, interruptions, or discontinuation of study treatment due to any reason.

OS will be estimated using the Kaplan-Meier method. The median OS along with 95% confidence interval will be presented.

Improvement of RBC/platelets transfusion independence

Red blood cells (RBC)/Platelets transfusion independence rate is defined as the proportion of participants having received no RBC/Platelets transfusions during at least 8 consecutive weeks (see Section 8.3.1 for details).

The number and percentage of participants will be shown for the overall FAS and then also in only those with transfusion dependence at baseline (i.e \geq 3 units of transfusion within 8 consecutive weeks prior to start of treatment).

Percentages will be provided with exact 95% confidence intervals (Clopper CJ and Pearson ES 1934). For participants with at least one period of transfusion independence, the total duration of all transfusion independence periods will be also summarized.

The duration of the transfusion independence is defined from the end date of the last transfusion received until the date transfusions are given again or last treatment in case transfusions had not (re-)started during treatment.

Immunogenicity analysis

Immunogenicity will be characterized descriptively by tabulating ADA prevalence at baseline and ADA incidence on-treatment.

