The duration of response will be derived for participants treated with sabatolimab at 800 mg Q4W who achieve HI or better (prior to any new antineoplastic therapy, including HSCT) as per investigator assessment and is defined from the first occurrence of CR, mCR, PR or HI until relapse, progression or death due to any reason.

Relapse, progression or death occurring after HSCT will be considered as an event for the duration of response. The date of the event will be the date of relapse, progression, or death whichever occurs first. If the participant did not relapse, progress or die, the duration of response will be censored at the last adequate response assessment. If the participant started a new antineoplastic therapy without prior documented relapse or progression, the duration of response is censored at the last adequate assessment prior to the start of that therapy and thus any subsequent relapse, progression, or death will not be considered as an event for duration of response.

Duration of response will be estimated using the Kaplan-Meier method. The median duration of response along with 95% confidence interval will be presented.

Time to CR/mCR

The time to CR/mCR will be derived for all participants treated with sabatolimab at 800 mg Q4W and is defined from start of treatment to first occurrence of CR/mCR (prior to any new antineoplastic therapy, including HSCT). For participants who reached CR /mCR after HSCT or a new antineoplastic therapy, the time to CR/mCR will be censored at the time of HSCT or initiation of new antineoplastic therapy.

For participants who did not reach CR/mCR, a). if they did not progress, die or progress to acute myeloid leukemia either, the time to CR/mCR will be censored at the last adequate response assessment; or b). if they progressed, died or the disease progressed to acute myeloid leukemia, the time to CR/mCR will be censored at the maximum follow-up (last participant last visit).

Time to CR/mCR will be estimated using the Kaplan-Meier method. The median time to CR/mCR along with 95% confidence interval will be presented.

Event-free survival (EFS)

Event-free survival (EFS) is defined from the date of start of treatment to:

- Lack of complete remission within the maximum of first 6 months or 6 cycles (including C7D1 assessment) of start of treatment
- Progression/Relapse
- Death from any cause

Whichever occurs first.

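### Time to CR/mCR is censored at HSCT or new therapy only for participants who respond afterwards, so leaving the risk set depends on a later outcome

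*Protocol*

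**What the plan says.** Protocol 12.5.1.2 defines time to CR/mCR for all participants treated at 800 mg Q4W, from start of treatment to the first CR or mCR before any new antineoplastic therapy or HSCT. Three censoring rules follow.

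- Response after a switch: "For participants who reached CR /mCR after HSCT or a new antineoplastic therapy, the time to CR/mCR will be censored at time of HSCT" or at the start of the new therapy.
- No response: "Participants who did not reach CR/mCR will be censored at last adequate response assessment".
- Progression, death or transformation to AML: maximum follow-up, meaning the last participant's last visit.

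The estimator is fixed: "Time to CR/mCR will be estimated using the Kaplan-Meier method", with a median and 95% confidence interval.

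SAP 2.6.1.2 keeps the first rule: "For participants who reached CR /mCR after HSCT or a new antineoplastic therapy, the time to CR/mCR will be censored at the time of HSCT". It then splits participants who never reached CR/mCR in two. Those without progression or death are censored at the last adequate response assessment. For the rest: "if they progressed, died or the disease progressed to acute myeloid leukemia, the time to CR/mCR will be censored at the maximum follow-up". Neither branch mentions HSCT or new therapy.

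The expansion part was not opened (SAP section 1), so this endpoint rests on cohort 2, planned at about 12 participants. SAP 2.6.1.2 makes Kaplan-Meier output depend on follow-up and number of events, but individual times and event or censoring types are listed in any case.

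**The concern.** Take two participants who start HSCT or a new therapy on the same day, neither with a prior CR/mCR or progression. The one who responds later is censored that day. The one who never responds stays in the risk set. Only their subsequent course separates them.

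Kaplan-Meier requires that leaving the risk set at a given time depends only on what is known by then. Here the censoring date cannot be assigned until the post-switch outcome is known. The estimate of response on study treatment then moves with the efficacy of the next therapy, and time under that therapy counts as non-response time on the triplet.

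The situation can arise. HSCT is a listed reason to stop treatment (Protocol 9.1.1). Participants who stop without progression continue efficacy assessments until progression, death, loss to follow-up or withdrawal of consent (Protocol 9.1.1.2), and starting a new therapy does not end that follow-up. Responses after a switch can therefore be recorded.

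**Working it through.** The documents give no numerical result for this endpoint, so there is none to reproduce. The check compares three rules for participants who switch before CR/mCR and before progression:

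- **A, as written:** later responders are censored at the switch; non-responders stay at risk.
- **B:** all are censored at the switch.
- **C:** all stay at risk to maximum follow-up, so switching acts as a competing event.

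**Hand example (assumed data, 12 participants).** Four respond at month 2. Four switch at month 3, of whom two later respond and two do not and later progress. Two respond at month 6. Two are censored at month 24. The Kaplan-Meier probability of response by month 6 is 1 minus the product of (1 − events/at risk):

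- A: six at risk at month 6, so 1 − (8/12)(4/6) = 55.6%.
- B: four at risk, so 1 − (8/12)(2/4) = 66.7%.
- C: eight at risk, so 1 − (8/12)(6/8) = 50.0%.

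**A single switcher (assumed data).** Four of 12 respond at month 2, one participant switches at month 3, two respond at month 6, and five are censored later.

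- If the switcher never responds and remains at risk past month 6, rule A gives 1 − (8/12)(6/8) = 50.0%.
- If the switcher later responds, rule A censors at month 3 and gives 1 − (8/12)(5/7) = 52.4%.

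On-treatment data are identical in the two cases. The 2.4 points come only from what happened after the switch.

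**Simulation (400,000 participants per setting; all inputs assumed).** Latent time to response is exponential with median 6 months. The progression or death hazard is 0.02 per month. The switch hazard is 0.01, 0.03 or 0.06 per month. The probability of response after a switch is 20%, 50% or 80%. Of post-switch non-responders, 60% later progress or die and the rest are last assessed 12 months after the switch. Maximum follow-up is 36 months. Participants who progress first go to maximum follow-up under all three rules.

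Estimated probability of response by month 12:

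| Switching | A, later response 20% / 50% / 80% | B | C |
|---|---|---|---|
| 7% | 66.1 / 67.0 / 67.6% | 68.2–68.3% | 65.5–65.7% |
| 18% | 61.6 / 63.5 / 65.9% | 67.6–67.7% | 60.2–60.3% |
| 31% | 55.4 / 58.8 / 63.1% | 66.7% | 53.4–53.5% |

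Rule A lies between B and C in every setting.

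- Shortfall against B: at 7% switching, from 68.2 − 67.6 = 0.6 to 68.2 − 66.1 = 2.1 points; at 31%, from 66.7 − 63.1 = 3.6 to 66.7 − 55.4 = 11.3 points.
- Excess over C: at 31% switching, from 55.4 − 53.5 = 1.9 to 63.1 − 53.4 = 9.7 points.

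**The case against.** **A pre-therapy limit may be implied.** The endpoint counts only responses before new therapy or HSCT. Protocol 12.4.3 and SAP 2.5.3.1 restrict the assessments used for CR to that period, in the same paragraph that defines adequacy. If the restriction carries over, a non-responder who switches and does not progress is censored at the last pre-switch assessment, and most of the gap closes for that participant. However, the definition itself, "An adequate response assessment is considered any disease assessment indicating response status apart from" unknown or not done, sets no time limit, and none is written for this endpoint. The SAP writes one for the three duration endpoints, EFS and LFS. It does not for PFS, so silence alone does not settle the reading. Even with the limit, non-responders who switch and later progress or die still go to maximum follow-up.

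**Reach.** A reader might infer that everyone who starts HSCT or new therapy before CR/mCR is affected. The documents do not support that. Efficacy follow-up ends at progression (Protocol 8.3.1), so someone who progresses and then switches has no scheduled response assessment and would normally go to maximum follow-up whatever follows.

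**The maximum-follow-up rule.** A reader might also conclude that every participant without CR/mCR should be censored when a new therapy starts. That would override the rule keeping participants who progressed first in the risk set. That rule is a coherent competing-event convention, and overriding it would remove treatment failures and raise the estimate.

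**Consequence.** This is a secondary endpoint with no test, and Kaplan-Meier output may not be produced. With 12 participants, sampling error dominates a few points: the exact 95% interval for 6/12 is about 21% to 79%. This limits the importance of the point but does not make the rule correct.

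**Conclusion.** The point holds in a limited form. For participants who switch with neither prior CR/mCR nor prior progression, both documents let a later outcome set the censoring date. The response probability is biased downward against censoring every switcher at the switch and upward against the competing-event cumulative incidence.

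The size depends on the switching rate and the post-switch response rate, which the documents do not give. Under the stated assumptions, the 12-month shortfall against uniform censoring is about 1 to 2 points at 7% switching and up to about 11 at 31%. These figures use the text as written; a pre-therapy limit on adequate assessments would reduce them.

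It would go too far to say that the reported Kaplan-Meier estimate will be materially wrong, since it may not be produced and the number of switchers is unknown. The primary CR rate is unaffected: CR after new therapy or HSCT is disregarded there for everyone. What remains certain is that the derived times and listed censoring types follow this rule.

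**What to change.** Amend the time to CR/mCR text in SAP 2.6.1.2 before database lock so that the first event sets the rule and later response never does:

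- Participants who start HSCT or a new antineoplastic therapy without prior CR/mCR and without prior progression are all censored at that start date, whatever follows.
- Participants who progress or die before any HSCT or new therapy keep the maximum-follow-up rule, even if they later switch or respond.
- Other participants without CR/mCR are censored at the last adequate response assessment, as now.

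The estimand should be named: time to response on study treatment, with earlier progression and death as competing events and switching censored. Keeping all switchers to maximum follow-up would also be coherent. Censoring is the smaller change, because the present text already does it for later responders.

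The cost is one sentence and one derivation condition. No protocol amendment is needed; SAP section 3 can record the departure from Protocol 12.5.1.2. The downside is that follow-up is shortened for a few switchers who never respond, and the estimated response probability may rise slightly.
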